## APPENDIX 2. HAMMERSMITH FUNCTIONAL MOTOR SCALE-EXPANDED

Smartnet & PNCR		Hammersmith Functional Motor Scale for SMA (HFMS)					07/03/09
Name _____		DOB _____					
Date of assessment _____		Time taken to complete _____					
Date of spinal surgery _____		Evaluator _____					
Please circle highest current level of independent mobility							LBC = Limited by contracture
None	Rolls	Bottom shuffles	creeps /crawls	Walks with crutches / frame /rollator	Walks with KAFO's / AFO's	Independent walking	
Comment.....							
Test	Instruction	2	1	0	L B C	S =	Comments S = score
1 Plinth /chair sitting Can be over edge of plinth or on plinth / floor. Record best you see	Can you sit on the plinth /chair without using your hands for support for a count of 3? Back unsupported /feet +/- support)	Able to sit using no hand support for a count of 3 or more	Needs one hand support to maintain balance for a count of 3	Needs two hand support to maintain balance  Unable to sit			
2 Long sitting Legs straight = knees maybe flexed, knee caps pointing upwards, ankles <10cm apart	Can you sit on the floor/plinth without using your hands for support and with your legs straight for a count of 3?	Able to sit on floor/plinth with legs straight without hand support for a count of 3	Able to sit on floor/plinth with legs straight propping with one hand support for a count of 3	Able to long sit using two hands for a count of 3  Or unable to sit with straight legs			
3 One hand to head in sitting Hand touch head above level of ears	Can you get one hand to your head without bending your neck	Able to bring one hand to head. Head and trunk remain stable	Can only bring hand to head by flexing head	Unable to bring hand to head even using head and trunk movement			R / L
4 Two hands to head in sitting  Hands touch head above level of ear	Can you lift both hands up at the same time, to your head, without bending your neck?	Able to place both hands on head arms free from side. Head and trunk remain stable	Able to place hands on head but only using head flexion or side tilt or crawling hands up or one at a time	Unable to place both hands on head			
5 Supine to side-lying	Can you roll onto your side in both directions? Try not to use your hands	Able to ½ roll from supine both ways	Can ½ roll only one way R / L	Unable to half roll either way			Shoulders perpendicular to floor. Trunk and hips in line with body

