#### 2.2.2. Additional Safety and Efficacy Analysis

An additional analysis of efficacy and safety data was conducted once the last Cohort 2 patient completed the 12 month visit.

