The primary efficacy endpoint for the group of patients  $\geq$  6 months and  $<$  24 months of age at time of dosing will be the proportion of patients who achieve the ability to stand alone up to the 12-month study visit. Twenty-four (24) children aged  $\geq$  6 months and  $<$  24 months will be enrolled, with twelve (12) children receiving Dose B and twelve children receiving Dose C. The proportion of patients developing the ability to stand alone will be compared with a cohort of eligibility-matched patients from the PNCR natural history study of SMA; this comparison will be conducted for Dose B only. Based upon a review of eligibility-matched patients from the PNCR, fourteen percent (14%) of patients who meet the study criteria for patients  $\geq$  6 months and  $<$  24 months of age achieved the ability to stand alone, and ten percent (10%) achieved the ability to walk alone. It is expected that 85% of treated patients  $\geq$  6 months and  $<$  24 months of age will achieve the ability to stand alone and 60% will achieve the ability to walk alone. With this efficacy, a sample size of 12 patients would provide power of  $>$  90% to detect a significant difference compared with the matched control cohort with  $\alpha = 0.05$  using a two sample 2-sided Fisher exact test.

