### 5.5.2. Per Protocol Analysis Set

The Per Protocol (PP) Analysis Set consists of all enrolled patients who are given an AVXS-101 intrathecal injection and who did not have any major protocol violations which may have

impacted their efficacy or safety data. The determination of the criteria for which patients will be excluded from the PP Set will occur prior to database lock of the study. Specifically, if there is evidence at Screening that a patient is able to walk with support (according to Bayley-III Gross Motor Subtest #37) or that a patient does not have any clinical symptoms of SMA, they will be excluded from the PP Set.

The PP Set will be used for a sensitivity analysis of the primary efficacy endpoint of each cohort.

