### 5.6.1. Primary analyses vs. PNCR

For the cohort of patients  $\geq$  6 months and  $<$  24 months of age, patient-level data from a cohort of 51 patients drawn from the PNCR Network natural history study of SMA will serve as a “population-matched” control cohort. This comparison cohort encompasses all 51 patients enrolled in the PNCR study who met the criteria of having SMA Types 2 or 3, 3 copies of *SMN2* and symptom onset before 12 months of age and had at least one visit at or before 36 months of age. Of this cohort, 7/51 (14%) of the natural history cohort attained the ability to stand alone (defined as achieving a score of 2 on item #19 of the HFMSE). 5/51 (10%) attained the ability to walk alone (defined as achieving a score of 2 on item #20 of the HFMSE).

For the cohort of patients between 24 and  $<$  60 months of age, patient-level data from a cohort of 15 patients drawn from the PNCR Network natural history study of SMA will serve as a “population-matched” control cohort for the primary analysis. This comparison cohort encompasses all 15 patients enrolled in the PNCR study who met the criteria of having SMA Types 2 or 3, 3 copies of *SMN2*, symptom onset before 12 months of age, diagnosis before 24 months of age and unable to stand or walk at enrollment (baseline visit) and who received a HFMSE evaluation between 24 and 60 months of age (“baseline”), and a follow-up evaluation

(HFMS or HFMSE) performed between 12 and 14 months following that baseline evaluation. It is stated in the protocol that among the patients in this cohort, a mean change of -1.33 points (Standard deviation=4.32) was seen in HFMS. However, the primary endpoint for this cohort is HFMSE, not HFMS. As such, the comparison to PNCR will utilize HFMSE. Among patients in this PNCR cohort, a mean change of -1.13 points (Standard deviation=4.90) was seen in HFMSE, in line with other publications describing disease progression in SMA type 2 and 3 patients (Kaufman et al 2012, Mercuri et al 2016). From this point forward, this PNCR comparator group of 15 patients will be referred to as the “Primary PNCR” group.

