## 6. GENERAL ASPECTS FOR STATISTICAL ANALYSIS

### 6.1. General Methods

In general, descriptive statistical methods will be used to summarize the data from this study. Hypothesis testing will be performed for the efficacy endpoints based upon the predetermined sample sizes. Unless stated otherwise, the term “descriptive statistics” refers to number of patients (n), mean, median, standard deviation, minimum, and maximum for continuous data and frequencies and percentages for categorical data. Unless noted otherwise, the data will be sorted first by dose (Dose A, then Dose B, then Dose C), age group, patient number, and then by date within each patient number.

Unless noted otherwise, all safety tables will be summarized using the SS, by the actual dose received and by age group.

All descriptive statistics of efficacy tables will be summarized by the assigned dose and age group. The efficacy analyses will be performed to compare with the efficacy endpoints of patients assigned to AVXS-101 and patients drawn from a widely (peer-reviewed) published natural history dataset collected by the PNCR network; comparisons to the PNCR data will be conducted for Dose B only. Efficacy data for Dose A and Dose C will only be summarized descriptively and will not be compared to the PNCR data.

Efficacy analyses will be conducted on the ITT or ECAS as specified within each section, with analyses on the ECAS produced only if the ECAS contains a subset of patients of the ITT. Since the FAS and the ITT Set include the same patients (SAP Section 5.3), the ITT Set is used to represent the efficacy analyses by the FAS stated in the protocol.

Unless specified otherwise, all statistical testing and confidence intervals (CI) will be 2-sided and will be performed using an alpha level of 0.05. No adjustments for multiple comparisons will be made.

All statistical analyses will be conducted with the SAS® software package version 9.4 or higher.

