### 8. EFFICACY

#### 8.1. Primary Efficacy Endpoints and Analysis

##### 8.1.1. Proportion of patients $\geq$ 6 months and $<$ 24 months at time of dosing that achieve the ability to stand alone at any post-baseline visit up to 12 months

The developmental milestone stands alone as assessed by Bayley-III Gross Motor Subtest #40 will be assessed at the scheduled visits in accord with the Schedule of Assessments for evaluating patient’s ability to stand alone. The developmental milestone achievement of each patient in the study is based on the video evidence reviewed and confirmed by an independent central reviewer, as specified in SAP Section 6.4.3. The proportion of patients  $\geq$  6 months and  $<$  24 months of age at time of dosing that achieve the developmental milestone at any post-baseline visit up to 12 months will be summarized overall and by dose.

The proportion of patients achieving the corresponding developmental milestone “stand unsupported” assessed using the HFMSE item #19 within 12 months in the historical dataset of PNCR network will also be included by the matched age group. PNCR patients with an HFMSE item #19 score of 2 at either the Baseline visit or at any post-Baseline visit within 12 months of Baseline will be considered to have achieved the milestone. The HFMSE will not be started until patients reach 24 months of age; however, the Bayley-III will be assessed at Screening and all study visits as indicated in the Schedule of Assessments. An additional summary will be produced to present the proportion of patients achieving the developmental milestone at each visit; this will be summarized overall and by dose.

The corresponding p-value from Fisher’s exact test will be computed for the comparison between AVXS-101 Dose B and PNCR data and this is the primary analysis for this endpoint. The summary and statistical analysis will be conducted using the ITT Set and will be repeated using the PP Set as a sensitivity analysis. The difference of the proportions between AVXS-101 and PNCR will be summarized and the exact 95% CIs will be provided accordingly.

As a supporting analysis to the primary analysis, the time to achieving ability to stand alone will be summarized for patients overall and by dose in the ITT Set. The study day will be used as the

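### In the younger group, the Per Protocol sensitivity analysis screens treated children for supported walking but applies no matching function limit to the 51 PNCR controls

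*SAP*

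**What the plan says.** SAP 5.5.2 defines the PP Set among injected patients without major protocol violations that may have affected their data. It leaves the exclusion criteria to be settled before database lock, but names two: a child is out "if there is evidence at Screening that a patient is able to walk with support (according to Bayley-III Gross Motor Subtest #37" is the item concerned, or if the child has no clinical symptoms of SMA. It states no corresponding rule for PNCR patients.

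SAP 8.1.1 says that the younger-group primary analysis, Dose B against PNCR by Fisher's exact test, "will be repeated using the PP Set as a sensitivity analysis".

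On the control side, SAP 5.6.1 says "This comparison cohort encompasses all 51 patients enrolled in the PNCR study who met the criteria". Those criteria are SMA type 2 or 3, three SMN2 copies, symptom onset before 12 months and a visit by 36 months of age. None of them limits motor function. SAP 8.1.1 adds that a control scoring 2 on HFMSE item 19 at Baseline counts as having reached the milestone. For the older group, SAP 5.6.1 selects 15 controls who could not stand or walk at enrollment.

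On timing, SAP 2.2.2 (version 6.0) reports: "An additional analysis of efficacy and safety data was conducted once the last Cohort 2 patient completed the 12 month visit".

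**The concern.** Children who can already step with support are plausibly the closest to standing alone. The PP rule removes them from the treated side only. On the control side it leaves in any child of similar function, and also any child who already stands and is scored a success for it. A reader will take the PP table as a check on whether the ITT result survives a stricter population. With one side screened and the other not, a weaker PP result could reflect the filter and not the treatment, and a real effect could look fragile.

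**Working it through.** **The plan's own figure.** Inputs from SAP 3.7 and 5.6.1: 12 Dose B patients, 85% expected to stand, 14% in controls, 51 controls, two-sided Fisher test at 0.05. The SAP states that "With this efficacy, a sample size of 12 patients would provide power of" more than 90%. Summing the binomial probabilities of every table with Fisher p≤0.05 gives 99.9% for 12 versus 51. The stated power reproduces and is not in dispute.

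**What is not known.** The documents do not give the number of supported walkers in either group, or how many of the seven control achievers already stood at Baseline. Let k be the treated responders removed by the PP rule and c the control achievers removed by a matching rule. With x treated responders, the comparison is (x−k)/(12−k) versus (7−c)/(51−c). I take 7/51 as the control result. SAP 5.6.1 gives it without a time limit, while 8.1.1 counts achievement within 12 months of Baseline.

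**Two-sided Fisher p-values**

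| Scenario | ITT | PP as written | PP with controls also restricted |
|---|---|---|---|
| x=10, k=2 (near the planned 85%) | 10/12 v 7/51, p<0.0001 | 8/10 v 7/51, p=0.0001 | c=5: 8/10 v 2/46, p<0.0001 |
| x=6, k=2 | 6/12 v 7/51, p=0.012 | 4/10 v 7/51, p=0.070 | c=2: 4/10 v 5/49, p=0.036 |
| x=5, k=1 (fewest responders significant in ITT) | 5/12 v 7/51, p=0.041 | 4/11 v 7/51, p=0.094 | c=2: 4/11 v 5/49, p=0.0498; c=5: 4/11 v 2/46, p=0.010 |

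With x=10, removing three treated responders still gives 7/9 v 7/51, p=0.0002.

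**Sensitivity to who is removed.** In the x=6, k=2 case, suppose the matching rule removes four controls. If all four are achievers, the result is 4/10 v 3/47, p=0.014. If one is, it is 4/10 v 6/47, p=0.062. If none is, it is 4/10 v 7/47, p=0.088. If the PP rule removes a treated non-responder, the treated rate rises: 5/12 becomes 5/11 v 7/51, p=0.029.

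One part of the control side is not a guess. A control scoring 2 on item 19 at Baseline is an achiever by the rule in 8.1.1, so excluding such children can only lower the control rate. The direction against AVXS-101 is therefore likely, but it also assumes that the treated children removed would mostly have stood.

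**The case against.** The strongest reply is that this is one sensitivity table, that its likely error is conservative, and that the ITT primary is untouched. All of that stands, and it sets the severity.

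A reader might also infer stronger points that the documents do not support:

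- *The one-sided filter reverses the conclusion.* It does so only for selected counts near the threshold. With non-achievers among the removed controls, matching need not restore significance (p=0.088 above), and near the planned effect nothing changes.
- *The older comparison has the same fault.* Its 15 controls had to be unable to stand or walk at enrollment. Whether that wording admits supported walkers is not stated, so the asymmetry there is unclear.
- *The supported-walking rule was chosen after Dose B results.* The rule is written into 5.5.2. A PP definition entered in version 5.0 (November 2019), whose change log describes the Cohort 2 analysis as still to come. Version 6.0 says it clarified the definition and reports that analysis as done. The documents do not show which version first held the walking rule, so post hoc choice is possible but not shown. Only the residual category of major violations is still open.
- *Supported walkers were plainly eligible, so the exclusion is not a per-protocol one.* Protocol 8.1 criterion 4 and 8.2 criterion 1 refer to independent standing or walking, but 8.1 criterion 1 says the child cannot stand or walk, without that qualifier. Either reading is arguable.
- *The same filter can simply be run on PNCR.* Bayley scores are not available there (SAP 19.3). HFMSE item 18 is supported standing and item 20 is unaided stepping, so neither measures supported walking. The form in Protocol Appendix 2 has a mobility line with entries such as "Walks with crutches / frame /rollator", but nothing shows that it was kept in the PNCR data or that it matches Bayley item 37.

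**Conclusion.** The point holds for the younger group. As written, the PP comparison sets function-screened treated children against controls with no function limit, some of whom may count as achievers from Baseline, so it is not a like-for-like check of the primary result. The lack of a functional ceiling belongs to the primary control definition; the PP rule adds a further imbalance to it. The likely bias is against AVXS-101. It matters to the p-value only if the Dose B response is near the threshold (5 or 6 of 12 in the scenarios shown) and the children removed are mostly responders. At about the planned response the reading is unchanged. These sizes rest on assumed counts. Severity is minor.

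**What to change.** In SAP 8.1.1, report the Dose B PP comparison twice, against the unrestricted PNCR controls and against controls restricted at their baseline, with n for each. The restriction should exclude at least controls who stand or step unaided at baseline (HFMSE items 19 and 20). If the form's mobility line was retained in the PNCR data, it should also exclude those recorded as walking with crutches, frame or orthoses. State that this is a proxy because Bayley item 37 is not available in PNCR.

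In SAP 5.5.2, limit PP exclusions for Dose B to the two already listed, and label as post hoc any criterion set after the Cohort 2 Month 12 analysis.

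The cost is a few lines of SAP text, a check of which PNCR fields exist, and a smaller control n with an imperfect proxy in one sensitivity table. Some younger controls may lack an HFMSE at a comparable baseline, since the SAP describes the scale for age 24 months and above. Their number should be reported too.

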## 5.6. PNCR Population-Matched Control Population

A population-matched control cohort will be drawn from the PNCR Natural History dataset. The PNCR is a large natural history study developed from a cohort of 337 patients with any form of spinal muscular atrophy followed at 3 large, internationally recognized tertiary medical centers with significant expertise in the management of SMA (Harvard University/Boston Children's Hospital, Columbia University and the University of Pennsylvania/Children's Hospital of Philadelphia).

Previously identified patients with any form of SMA, of any age, followed in PNCR site clinics and newly diagnosed patients were enrolled. All eligible patients were offered participation. Study visits were scheduled at baseline and at 2, 4, 6, 9, and 12 months and every 6 months thereafter. The SMA standard of care guidelines published in 2007 were used as a basis for providing uniform care among the study sites.

For purposes of this study, sitting (for SMA-II) was defined as being able to sit independently for > 10 seconds, and walking alone was defined as having scored 2 points on item #20 of the HFMSE at any time. All patients with SMA type 2 or 3 who provided sufficient records and follow-up for evaluation and met the basic entry criteria for the two cohorts of the AVXS-101-CL-102 study (3 copies of *SMN2*, symptom onset before 12 months of age and baseline and follow-up visits within the age criteria for the study) were considered for possible inclusion in the natural history comparison dataset. The *SMN2* modifier mutation (c.859G>C) described by Prior and colleagues (Prior et al., 2009) was not assessed in the PNCR study cohort.

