### 8.2. Patient Exclusion Criteria

Patients must not meet any of the following exclusion criteria:

1. Current or historical ability to stand or walk independently
2. Contraindications for spinal tap procedure or administration of IT therapy (e.g., spina bifida, meningitis, impairment, clotting abnormalities, or obstructive spinal hardware preventing effective access to CSF space) or presence of an implanted shunt for the drainage of CSF or an implanted CNS catheter
3. Severe contractures as determined by designated Physical Therapist(s) at screening that interfere with either the ability to attain/demonstrate functional measures (e.g., standing, walking) or interferes with ability to receive IT dosing
4. Severe scoliosis (defined as  $\geq$  50° curvature of spine) evident on X-ray examination

5. Previous, planned or expected scoliosis repair surgery/procedure within 1 year of dose administration
6. Use of invasive ventilatory support (tracheotomy with positive pressure) or pulse oximetry < 95% saturation at screening while the patient is awake, or for high altitudes > 1000 m, oxygen saturation < 92% while the patient is awake
  - Pulse oximetry saturation must not decrease  $\geq$  four percentage points between screening and highest value on day of dosing
7. Use or requirement of non-invasive ventilatory support for 12 or more hours daily in the two weeks prior to dosing
8. Medical necessity for a gastric feeding tube, where the majority of feedings are given by non-oral methods (i.e., nasogastric tube or nasojejunal tube) or patients whose weight-for-age falls below the 3rd percentile based on World Health Organization (WHO) Child Growth Standards ([Onis 2006](#)). Placement of a permanent gastrostomy prior to screening is not an exclusion.
9. Active viral infection (includes human immunodeficiency virus [HIV] or serology positive for hepatitis B or C, or Zika virus)
10. Serious non-respiratory tract illness requiring systemic treatment and/or hospitalization within two weeks prior to study entry
11. Respiratory infection requiring medical attention, medical intervention or increase in supportive care of any manner within four weeks prior to study entry
12. Severe non-pulmonary/respiratory tract infection (e.g., pyelonephritis or meningitis) within four weeks before study dosing or concomitant illness that in the opinion of the Principal Investigator creates unnecessary risks for gene transfer such as:

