The primary efficacy endpoint for the group of patients  $\geq 6$  months and  $< 24$  months of age at time of dosing will be the proportion of treated patients who achieve the ability to stand without support up to the 12-month study visit. Twelve children aged  $\geq 6$  months and  $< 24$  months will be enrolled who receive Dose B. The proportion of patients developing the ability to stand without support will be compared with a cohort of eligibility-matched patients from the PNCR natural history study of SMA. Based upon a review of eligibility-matched patients from the PNCR, 14% of patients who meet the study criteria for patients  $\geq 6$  months and  $< 24$  months of age achieved the ability to stand without support, and 10% achieved the ability to walk without assistance. We expect 85% of treated patients  $\geq 6$  months and  $< 24$  months of age to achieve the ability to stand alone and 60% to achieve the ability to walk without support. With this efficacy a sample size of 12 patients would provide power of  $> 90\%$  to detect a significant difference compared with the matched control cohort with  $\alpha = 0.05$  using a two-sample 2-sided superiority Fisher exact test.

The primary efficacy endpoint will be the change in HFMSE in treated patients between 24 months and  $< 60$  months of age at time of dosing. Twelve children aged  $\geq 24$  months and  $< 60$  months will be enrolled. Change in HFMSE score at 12 months will be compared with a cohort of eligibility-matched patients from the PNCR natural history study of SMA. Based upon a review of eligibility-matched patients from the PNCR, a mean change of -1.33 points (standard deviation = 4.32 points) is seen at 12 months from baseline among patients aged 2-5 years at first evaluation with 3 copies of *SMN2* in the PNCR dataset. We expect to observe a mean increase

of 8 points from baseline on the HFMSE with equivalent variance. Based upon these assumptions, 12 patients between 24 and <60 months at enrollment will have >90% power to detect a significant difference with  $\alpha = 0.05$  when compared to patient-level data available from the PNCR dataset using two-sample ANOVA.

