### 7.2. Demographic and Other Baseline Characteristics

Demographics and baseline characteristics will be summarized for the PNCR dataset and separately for the SS overall and by dose and age group, with descriptive statistics including n, mean, standard deviation, median, minimum, and maximum for numeric variables and frequency and percentage for categorical variables.

The following characteristics will be summarized for the SS:

Demographics include age, gender, ethnicity, race, weight, length and body mass index.

Age (months) = (dose date - date of birth +1)/30

Length (cm) = Length (in inches) \* 2.54

Weight (kg) = Weight (in lbs) \* 0.4536

Race will be summarized as captured in the eCRF. Patients reporting multiple races will be summarized as 'Multiple'.

Baseline disease characteristics include the following:

- Familial history of SMA including affected siblings or parent carriers
- Gestational age at birth
- Length/weight and head circumference at birth
- Hospitalization information from time of birth including number, duration, and reason for hospitalizations including primary ICD-10 codes if available
- Historical ventilatory support, if any
- Historical feeding support, if any

All demographics and baseline characteristics will be listed for the SS.

The following characteristics will be summarized for each of the three PNCR populations being referenced in this study (refer to Section 5.6 of this SAP):

- Age at PNCR entry (months)
- Age (months) at first HFMSE assessment conducted after reaching 24 months of age
- Gender
- Ethnicity
- Race
- Gestational age at birth
- Height (cm) at PNCR entry
- Weight (kg) at PNCR entry

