## 19. APPENDICES

### 19.1. Hammersmith Functional Motor Scale - Expanded

Smartnet & PNCR		Hammersmith Functional Motor Scale for SMA (HFMS)					07/03/09
Name	DOB	Time taken to complete					
Date of assessment		Evaluator					
Date of spinal surgery							
Please circle highest current level of independent mobility							LBC = Limited by contracture
None	Rolls	Bottom shuffles	creeps /crawls	Walks with crutches / frame /rollator	Walks with KAFO's / AFO's	Independent walking	
Comment.....							
Test	Instruction	2	1	0	L B C	Comments S = score	
1 Plinth /chair sitting Can be over edge of plinth or on plinth / floor. Record best you see	Can you sit on the plinth /chair without using your hands for support for a count of 3? Back unsupported (feet +/- support)	Able to sit using no hand support for a count of 3 or more	Needs one hand support to maintain balance for a count of 3	Needs two hand support to maintain balance		Item 1 Predominant spinal posture 	
2 Long sitting Legs straight = knees maybe flexed, knee caps pointing upwards, ankles <10cm apart	Can you sit on the floor/plinth without using your hands for support and with your legs straight for a count of 3?	Able to sit on floor/plinth with legs straight without hand support for a count of 3	Able to sit on floor/plinth with legs straight propping with one hand support for a count of 3	Able to long sit using two hands for a count of 3 Or unable to sit with straight legs		Predominant leg posture 	
3 One hand to head in sitting Hand touch head above level of ears	Can you get one hand to your head without bending your neck	Able to bring one hand to head. Head and trunk remain stable	Can only bring hand to head by flexing head	Unable to bring hand to head even using head and trunk movement		R / L	
4 Two hands to head in sitting Hands touch head above level of ear	Can you lift both hands up at the same time, to your head, without bending your neck?	Able to place both hands on head arms free from side. Head and trunk remain stable	Able to place hands on head but only using head flexion or side tilt or crawling hands up or one at a time	Unable to place both hands on head			
5 Supine to side-lying	Can you roll onto your side in both directions? Try not to use your hands	Able to ½ roll from supine both ways	Can ½ roll only one way R / L	Unable to half roll either way		Shoulders perpendicular to floor. Trunk and hips in line with body	

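### The PNCR controls are called eligibility-matched, but no severity exclusion (nor, for the 51 younger controls, any baseline motor criterion) is applied to them; the bias could run either way

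*SAP*

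**What the plan says.** Protocol 14.4 says the younger group's standing rate will be "compared with a cohort of eligibility-matched patients from the PNCR natural history study of SMA" and gives 14% as the rate among controls meeting the study criteria. SAP 3.7 repeats this for both age groups.

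SAP 5.6 gives the general filter: SMA type 2 or 3, sufficient records, and patients who "met the basic entry criteria for the two cohorts of the AVXS-101-CL-102 study", followed by the three criteria meant. SAP 5.6.1 and 5.6.2 then define three groups:

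- **51 younger controls:** type 2 or 3, three SMN2 copies, onset before 12 months, at least one visit by 36 months of age.
- **15 older controls (Primary PNCR):** the same type, genotype and onset, plus diagnosis before 24 months, unable to stand or walk at enrollment, and HFMSE timing rules.
- **17 older controls (Sensitivity PNCR):** matched as closely as possible; sitting without support, not standing or walking.

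For the treated children, Protocol 8.1 requires independent sitting and a negative modifier test. Protocol 8.2 excludes current or past standing or walking (exclusion 1) and, in exclusions 3 to 8, severe contractures, severe scoliosis, scoliosis surgery, ventilation or low oxygen saturation, mainly non-oral feeding, and low weight-for-age. The contracture rule is tied directly to the endpoint: "Severe contractures as determined by designated Physical Therapist(s) at screening that interfere with either the ability to attain/demonstrate functional measures (e.g., standing, walking".

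**The concern.** There is no concurrent control arm, so each AVXS-101 versus PNCR p-value is only as good as the similarity of the two groups. The label tells the reader that similarity was secured by applying the trial's criteria. The listed filters do not support that.

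The gap matters most for the younger group. A child whose contractures prevent standing is almost certain to be a non-stander, and can be counted only on the control side. Conversely, a child who already stands at baseline cannot enter the trial, yet under SAP 8.1.1 counts as a control success; SAP 8.2.1 does the same for walking. Standing is this group's primary endpoint, and no alternative control set is planned for it.

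SAP 5.6.2 shows the gap is not merely theoretical: one of the 15 Primary PNCR controls has an HFMSE score of 0 at every visit. On item 1 of the scale, 0 means two-hand support is needed or the child cannot sit. As recorded, that child fails the trial's sitting criterion but stays in the primary comparison.

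**Working it through.** **Inputs.** Treated n = 12 (SAP 3.7: "a sample size of 12 patients would provide power of" more than 90%). Treated rates: 85% standing ("It is expected that 85% of treated patients") and 60% walking. Younger controls: 7/51 stand and 5/51 walk (SAP 5.6.1). Older controls: mean HFMSE change -1.13, n = 15. Test: two-sided Fisher; under SAP 6.1 "all statistical testing and confidence intervals (CI) will be 2-sided and will be performed using an alpha level of 0.05".

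**Formulas.** With x successes of 12 treated and y of n controls, the table probability given the margins is C(12,x)·C(n,y)/C(12+n,x+y). The two-sided p sums this over all tables with the same margins that are no more probable than the one observed. Power sums Bin(x;12,p1)·Bin(y;n,p2) over tables with p ≤ 0.05 and x/12 > y/n.

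**The plan's own figure.** Against 51 controls, power is 99.9% for standing (85% v 14%) and 94.3% for walking (60% v 10%). The stated figure of more than 90% reproduces.

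**What each gap could do to standing.** The documents do not say how many controls are ineligible, so the removals below are assumptions.

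| Assumed removal | Controls | One fewer treated stander | Minimum needed |
|---|---|---|---|
| none | 7/51 | 4/12, p=0.197 | 5/12, p=0.041 |
| 5 non-standers | 7/46 | 5/12, p=0.102 | 6/12, p=0.018 |
| 10 non-standers | 7/41 | 6/12, p=0.0503 | 7/12, p=0.008 |
| 3 baseline standers | 4/48 | 3/12, p=0.135 | 4/12, p=0.043 |
| 10 non-standers and 3 baseline standers | 4/38 | 4/12, p=0.082 | 5/12, p=0.027 |

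The last row combines the two kinds of removal (51-10-3 = 38; 7-3 = 4) and returns to the planned threshold. The two gaps can offset each other, but only the data can show whether they do.

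**Power after removing k control failures, responders kept.**

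- Standing: k=10 gives 99.5%, k=20 gives 97.7%. Power first falls below 90% at k=27 (7/24, 88.9%), out of 51-7 = 44 non-standers.
- Walking: k=0 gives 94.5%, k=10 gives 87.3%, k=20 gives 77.2%. Power first falls below 90% at k=9 (5/42, 89.2%).

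**HFMSE, the one documented case.** Dropping the child with zero change gives -1.13 × 15/14 = -1.21. The control decline becomes slightly larger, so keeping this child works slightly against AVXS-101.

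**The case against.** A reader might infer that only genotype, onset and age were matched, that sicker controls count as failures throughout, and that the comparison therefore favours AVXS-101. The documents do not support that.

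- **More was applied.** SMA type is required throughout. The 15 also needed diagnosis before 24 months and no standing or walking at enrollment. The 17 had to sit, and SAP 8.1.2, 8.2.1 and 8.4 already plan sensitivity analyses with them.
- **The direction is not shown.** Baseline standers count as control successes, and SAP 5.6 says the SMN2 modifier was not assessed in PNCR. Both can raise control performance.
- **HFMSE does not follow the failure argument.** A child at the floor cannot decline. For removal of 3 of the 15 to shift the control mean by 1 point, those three would have to average (15×(-1.13) - 12×(-0.13))/3 = -5.13 points; nothing in the documents suggests this. The planned model also adjusts for baseline HFMSE and age.
- **Standing is robust at the assumed effect.** At 85%, about 0.85×12 = 10.2 treated children stand, well above 7.
- **Some fields may not exist.** The heading "LBC = Limited by contracture" and the spinal-surgery date appear on a blank form in SAP 19.1. A contracture mark on an item is also not a therapist's judgement of severe contracture. SAP 7.2 lists "Weight (kg) at PNCR entry", which need not be weight at the analysis baseline.

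All of this stands, and it removes any claim about direction. It leaves the unsupported label and the missing sensitivity set for the younger group. High power at 85% does not protect a conclusion drawn from a smaller observed response.

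**Conclusion.** The eligibility-matched label goes beyond the criteria listed. No severity exclusion is stated for any PNCR group. For the 51 younger controls, sitting without current or past standing or walking is not required at baseline. The number of ineligible controls and the net direction of bias are unknown.

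Under the assumed counts, the standing threshold ranges from 4/12 to 7/12 around the planned 5/12. That would matter only if the observed response falls in that range. Younger-group walking has less margin: nine removed failures take its power below 90%. These figures take 7/51 and 5/51 as the analysed control counts and rest on assumed removals; they are not estimates of bias. For HFMSE the documents give no basis for a stated size, and their one concrete case moves the mean by only 0.08 points.

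This should be corrected because it limits what the external comparison can show. It does not establish that the comparison is biased towards AVXS-101.

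**What to change.** 1. In SAP 5.6.2, pre-specify a sensitivity analysis of standing and walking for the younger group. Restrict it to PNCR controls who at baseline sit, do not stand or walk and have no record of having done so, and who meet Protocol 8.2 exclusions 3 to 8 wherever PNCR holds the field. Non-standing and non-walking can be read from the baseline HFMSE items 19 and 20 that SAP 8.1.1 and 8.2.1 already use; state the scores that define them.
2. Derive WHO weight-for-age from age, sex and weight at PNCR entry; SAP 11.5 already uses the WHO standard for treated patients. Use contracture marks and spinal-surgery date only if they are in the extract.
3. Apply the same recorded exclusions to the 15 and 17 older controls.
4. Report how many controls each rule removes, separating milestone achievers from non-achievers so that the direction becomes visible.
5. In Protocol 14.4 and SAP 3.7, replace the label with the criteria actually applied. Name what cannot be checked: ventilation (SAP 11.11 says the data were not collected), the modifier, and any field missing from the extract.

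The primary analysis is unchanged. The cost is SAP wording, a check of which fields are held, and fewer controls with a wider interval in the sensitivity analysis only.
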